#### **Psoriasis Area and Severity Index (PASI)**

Assessment of psoriasis based on severity of erythema, infiltration, and desquamation as well as area of involvement.

#### PASI 50 Response

A 50% or greater improvement from baseline in PASI score.

#### PASI 75 Response

A 75% or greater improvement from baseline in PASI score.

#### PASI 90 Response

A 90% or greater improvement from baseline in PASI score.

#### **Psoriasis Symptom Inventory (PSI)**

A measurement of a subject's severity of psoriasis signs and symptoms on an 8-item questionnaire (itch, redness, scaling, burning, stinging, cracking, flaking, pain). Each item is scored from 0 (not at all severe) to 4 (very severe). A 7-day recall period will be utilized and the PSI will be completed by the subject on paper version at baseline and weeks 1, 2, 3 and then at each visit.

#### Serious Event

An adverse event or infection that is fatal, life-threatening, requires in-patient hospitalization, results in persistent/significant disability, or is a congenital anomaly/birth defect or other significant medical hazard.

#### Static Physician Global Assessment (sPGA)

Assessment of psoriasis based on severity of induration, scaling, and erythema.

#### sPGA Clear or Almost Clear Status

A score of 0 (clear) or 1 (almost clear) on the sPGA assessment.

#### sPGA 0, 1, or 2 Status

A score of 0, 1, or 2 on the sPGA assessment.

#### sPGA 1 Grade Improvement From Baseline

An improvement on the sPGA assessment of at least 1 point.

#### sPGA 2 Grade Improvement From Baseline

An improvement on the sPGA assessment of at least 2 points.

#### **Study Completion Date**

The date of the last subject's last visit is the date of study completion.

#### Study Day

The number of days from Study Day 1, inclusive, given by the following formula:

Study Day = (Date of Interest – Date of Study Day 1) + 1

#### Study Day 1

The first day of investigational product administration.

#### **Study Treatment Period**

The time between the first dose of investigational product and the date of the subject's last visit (approximately 6 months).

#### Subject Incidence Rate

The subject incidence rate for a given event in a given time period is defined as the number of subjects with at least one reported occurrence of the event divided by the number of subjects who entered the time period. For subjects with multiple occurrences of the same event in a given time period, the event will only be counted once per subject.

#### **Treatment Emergent Adverse Event**

A treatment emergent adverse event is defined as an event that occurs after the initiation of investigational product or an event that is present prior to the initiation of investigational product but worsens either in intensity or frequency after the initiation of investigational product.

#### **Treatment Related Adverse Event**

A treatment related adverse event is defined as an event that is deemed by the investigator to be related to investigational product.

#### 7. Analysis Subsets

#### 7.1 Full Analysis Set

The full analysis set will include all subjects who received at least one dose of investigational product during the study. All safety and efficacy endpoints will be analyzed using the full analysis set.

#### 8. Interim Analysis and Early Stopping Guidelines

No interim analysis is planned for this study.

# 9. Data Screening and Acceptance

# 9.1 General Principles

The objective of the data screening is to assess the quantity, quality, and statistical characteristics of the data relative to the requirements of the planned analyses.

# 9.2 Data Handling and Electronic Transfer of Data

Amgen's Clinical Data Management department will provide all data to be used in the planned analyses. Data collection will be electronic and will be stored in the RAVE database. Laboratory data will be non-CTDB data located on the file server. Reasons for apremilast failure will be captured via IXRS and transferred to Data Management in SAS data format.

# 9.3 Handling of Missing and Incomplete Data

Subjects may be missing specific data points for a variety of reasons. In general, data may be missing due to a subject's early withdrawal from the study, a missed visit, or non-evaluability of an endpoint at a particular point in time. The general procedures outlined below describe what will be done when a data point is missing.

# 9.3.1 Missing Baseline Evaluation

Missing baseline evaluations will not be imputed.

# 9.3.2 Missing Post-baseline Evaluation

Subjects with missing post-baseline efficacy data will be imputed using the last observation carried forward (LOCF) method for the primary analysis for all efficacy endpoints. For LOCF imputation, missing post-baseline efficacy data will be carried forward from the last non-missing post-baseline value for that endpoint. Baseline efficacy data will not be carried forward to any missing post-baseline value.

For the primary endpoint, PASI 75 at week 12, missing post-baseline efficacy data will also be imputed using non-responder imputation as a sensitivity analysis. For non-responder imputation, the missing binary endpoint will be imputed with a value of zero to indicate no response. Patients without at least one post-baseline observation will also be defined as non-responders for the NRI analysis.

Missing post-baseline safety data will not be imputed.

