6.6 Excluded Treatments, Medical Devices, and/or Procedures During Study Period

Proscribed medications during this study include the following:

- Any biologic immune modulator (other than etanercept), including but not limited to alefacept, anakinra, adalimumab, infliximab, secukinumab, ustekinumab
- Apremilast
- Azathioprine
- Cyclophosphamide
- Cyclosporine
- Fumarates
- Hydroxyurea
- Leflunomide
- Live vaccines (eg, measles, mumps, and rubella; varicella; intranasal flu)

- Methotrexate
- Mycophenolate mofetil
- Oral or parenteral corticosteroids including intramuscular or intra-articular administration (the use of otic, nasal, or inhaled corticosteroids within recommended doses is allowed)
- Oral retinoids
- Sulfasalazine
- Systemically administered calcineurin inhibitors
- Tofacitinib
- Any other systemic therapy for psoriasis
- Any investigational therapy
- Thioguanine
- Topical steroids (exception: upper mid-strength or lower potency topical steroids are permitted on the scalp, axillae, and groin at the discretion of the investigator)
- Topical vitamin A or D analog preparations, or anthralin
- Topical cyclosporine or other calcineurin inhibitors
- PUVA therapy
- UVA therapy
- UVB therapy

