The sponsor is the exclusive owner of any data, discoveries, or derivative materials from the sample materials and is responsible for the destruction of the sample(s) at the request of the subject through the investigator, at the end of the storage period, or as appropriate (eg, the scientific rationale for experimentation with a certain sample type no longer justifies keeping the sample). If a commercial product is developed from this research project, the sponsor owns the commercial product. The subject has no commercial rights to such product and has no commercial rights to the data, information, discoveries, or derivative materials gained or produced from the sample. See Section 11.3 for subject confidentiality.

8. WITHDRAWAL FROM TREATMENT, PROCEDURES, AND STUDY 8.1 Subjects' Decision to Withdraw

Subjects have the right to withdraw from the study at any time and for any reason without prejudice to their future medical care by the physician or at the institution.

Subjects (or a legally acceptable representative) can decline to continue receiving investigational product and/or other protocol-required therapies or procedures at any time during the study but continue participation in the study. If this occurs, the investigator is to discuss with the subject the appropriate processes for discontinuation from investigational product or other protocol-required therapies and must discuss with the subject the options for continuation of the Schedule of Assessments (Table 1) and collection of data, including endpoints and adverse events. The investigator must document the change to the Schedule of Assessments (Table 1) and the level of follow-up that is agreed to by the subject (eg, in person, by telephone/mail, through family/friends, in correspondence/communication with other physicians, from review of the medical records).

Withdrawal of consent for a study means that the subject does not wish to receive further protocol-required therapies or procedures, and the subject does not wish to or is unable to continue further study participation. Subject data up to withdrawal of consent will be included in the analysis of the study, and where permitted, publically available data can be included after withdrawal of consent. The investigator is to discuss with the subject appropriate procedures for withdrawal from the study.

8.2 Investigator or Sponsor Decision to Withdraw or Terminate Subjects' Participation Prior to Study Completion

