8.3 Reasons for Removal From Treatment, or Study

8.3.1 Reasons for Removal From Treatment

Reasons for removal from protocol-required investigational product(s) or procedural assessments include any of the following:

- subject request
- safety concern (eg, due to an adverse event, ineligibility determined, protocol deviation, non-compliance, requirement for alternative therapy, pregnancy)
- death
- lost to follow-up
- decision by Sponsor (other than subject request, safety concern, lost to follow-up)

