# 5. Hypotheses and/or Estimations

A formal hypothesis will not be tested in this study. This study will estimate the proportion of subjects with PsO who achieve a PASI 75 after 12 weeks of treatment with etanercept following failure of treatment with apremilast.

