### 9.4 Detection of Bias

Factors that may bias the results of the study include:

- major protocol deviations likely to impact the analysis
- investigational product dosing compliance
- reasons for early withdrawal from treatment and from study

The incidence of these factors will be assessed. Major protocol deviations likely to impact the analysis and interpretation of the efficacy endpoints will be summarized in the clinical study report (CSR). If a significant number of major protocol deviations are observed, an additional sensitivity analysis may be performed on efficacy data excluding subjects with major protocol deviations.

In addition, a summary of IP dosing compliance will be provided. A sensitivity analysis including subjects who completed all scheduled doses of IP may be performed on PASI 50, 75, and 90 responses and sPGA 0 or 1 response to assess the potential bias of IP compliance if a significant IP non-compliance issue is detected.

Reasons for early withdrawal from treatment and early withdrawal from study will be summarized. If a significant pattern is observed, additional sensitivity analyses may be performed on efficacy data adjusting for reasons for early withdrawal.

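### Starting another psoriasis therapy has no pre-specified, mandatory analysis consequence, so a week 12 PASI 75 response observed afterwards counts as a response in the LOCF, observed-case and NRI analyses

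*SAP*

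**What the plan says.** - **Proscribed therapy.** Protocol 6.6 opens its list with "Proscribed medications during this study include the following" and names biologics, systemic psoriasis agents, phototherapy and most topicals. It sets no analysis rule.
- **Removal and staying on.** Protocol 8.3.1 includes "requirement for alternative therapy" among the examples of reasons for removal from etanercept or from assessments. Protocol 8.1 lets a subject decline etanercept "at any time during the study but continue participation in the study", with continued endpoint collection to be discussed.
- **Target.** SAP 5 estimates the proportion who "achieve a PASI 75 after 12 weeks of treatment with etanercept".
- **Endpoint.** SAP 6 defines PASI 75 as "A 75% or greater improvement from baseline in PASI score". SAP 7.1 analyses everyone who was dosed.
- **Missing data.** SAP 9.3 attributes missing data to withdrawal, missed visits or non-evaluability. Under LOCF (primary, SAP 9.3.2), "missing post-baseline efficacy data will be carried forward from the last non-missing post-baseline value for that endpoint". Under NRI (sensitivity, week 12 PASI 75), "For non-responder imputation, the missing binary endpoint will be imputed with a value of zero to indicate no response". The observed-case analysis uses what was recorded.
- **Nearest safeguard.** SAP 9.4 says that, if major deviations are numerous, "an additional sensitivity analysis may be performed on efficacy data excluding subjects with major protocol deviations". It also allows, again at discretion, an analysis restricted to subjects who completed all scheduled doses.
- **Data collection.** Protocol 6.3 collects start and stop dates for psoriasis therapies. Protocol 6.3 and 7.3.9 collect concomitant therapy only until treatment ends, while Table 1 lists it at every visit to Week 24/ET.

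**The concern.** The study has no control arm, and its product is a response rate attributed to 12 weeks of etanercept. A subject who starts another effective psoriasis treatment before week 12 and then shows a PASI 75 response would be counted toward that rate. One would expect at least the NRI analysis to set such a response aside, but as written it does not, because the value is not missing. The rate is then too high to the extent that these subjects would not have responded on etanercept alone, and no analysis that must be run would show by how much.

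**Working it through.** **1. Coding of one case.** A subject starts a proscribed systemic, biologic or phototherapy treatment before week 12, stays for assessments, and has a week 12 PASI at least 75% better than baseline.

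| Analysis | Week 12 PASI missing? | Coded |
|---|---|---|
| LOCF (primary) | No, rule not triggered | 1 |
| Observed cases | No, value used | 1 |
| NRI | No, rule not triggered | 1 |

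The three agree on this subject, so their comparison carries no information about it. If instead the last PASI after the other therapy is at week 8 and week 12 is missing, LOCF carries the response forward, NRI codes 0 and the observed-case analysis omits the subject. The blind spot is the observed value.

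**2. The plan's own precision (Protocol 10.2, SAP 3.2).** N = 80 and an assumed rate of 40%, so 32/80. Wald half-width: 1.96 × √(0.4 × 0.6/80) = 10.7 points. Wilson: 10.5. Exact (Clopper-Pearson): 29.2 to 51.6%, half-width (51.6 − 29.2)/2 = 11.2. The stated half-width below 15% and lower bound above 10% are both reproduced.

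**3. Size per case.** One case is 1/80 = 1.25 points overall. In the intolerability subgroup (10 to 20 subjects) it is 1/20 = 5 to 1/10 = 10 points.

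**4. Recoding s cases as non-responders.** Rate = (32 − s)/80, with exact 95% interval. The documents give no value for s; the range is an assumption, and all 80 subjects are taken as evaluable.

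| s | Rate | Exact 95% CI |
|---|---|---|
| 0 | 40.0% | 29.2 to 51.6 |
| 1 | 38.75% | 28.1 to 50.3 |
| 2 | 37.5% | 26.9 to 49.0 |
| 4 | 35.0% | 24.7 to 46.5 |
| 8 | 30.0% | 20.3 to 41.3 |
| 17 | 18.75% | 10.9 to 29.0 |
| 18 | 17.5% | 9.9 to 27.6 |

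The exact lower bound first falls below 10% at s = 18. The documents do not name the interval method: at s = 18 the Wald lower bound is 9.2% and the Wilson is 10.7%; Wilson first falls below 10% at s = 19 (9.7%).

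**5. Error in each direction.** Let f be the share of these subjects who would have responded on etanercept alone. The as-observed analysis overstates that rate by s(1 − f)/80; the non-responder rule understates it by s·f/80. For s = 2:

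| f | As observed | Non-responder rule |
|---|---|---|
| 0 | +2.5 points | 0 |
| 0.4 (planning rate) | +1.5 | −1.0 |
| 1 | 0 | −2.5 |

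The two errors are equal in size at f = 0.5.

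**6. What existing outputs would show.** The deviation table and list (SAP 10.3) may show that a case occurred, if proscribed therapy is one of the deviation categories, which are defined outside these documents. The concomitant-medication table (SAP 10.5.5) starts at 5% of subjects: 0.05 × 80 = 4, so a drug used by 3 of 80 (3.75%) is not shown. Neither output shows the effect on PASI 75.

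**The case against.** The strongest reply has four parts.

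- **SAP 9.4 is not silent.** A reader might infer that proscribed therapy has no consequence at all. The documents do not support that: deviations likely to affect the analysis are assessed and summarised, and two restricted analyses are allowed. The completers-of-all-doses analysis would drop anyone who stopped etanercept early. This part stands. What remains is that both analyses are discretionary, the triggers are not defined, and both remove subjects from the denominator rather than count them as non-responders.
- **The primary analysis need not change.** A reader might infer that the as-observed primary result is wrong and must be replaced. Using observed values regardless of other therapy is a legitimate target, and the documents do not choose between targets. By step 5, the non-responder rule has the larger error once f exceeds 0.5, and at f = 0.4 with two cases it only reduces the size of the error from 1.5 to 1.0 points. This part stands in full.
- **Cases should be few.** A case must start the therapy within 12 weeks, remain in assessments although the need for such therapy is a listed removal reason, and then respond. This stands, and it limits the size, but it does not supply a rule for a case that does occur.
- **The by-reason results are exploratory.** SAP Table 1 labels them so. That lowers the stakes of the 5 to 10 point figure, but SAP 10.4.5 commits to producing those results.

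**Conclusion.** The gap is real and modest. Under the rules as written, a week 12 PASI 75 response observed after another biologic, systemic or phototherapy treatment is kept in all three planned analyses, and no mandatory analysis shows its effect. The shift is 1.25 points per case overall and 5 to 10 points per case in the intolerability subgroup. Two cases, an assumed number, give 2.5 points at most, well inside the interval.

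A reader might infer that the conclusion resting on the 10% lower bound is threatened. It is not: starting from the planning rate of 40%, 18 of the 32 responders would have to be such cases (exact interval). What is affected is the point estimate and its descriptive interval, which are the study's stated product. All sizes assume 32/80 responders and 80 evaluable subjects; the true number of cases, and f, cannot be had from the documents.

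**What to change.** In SAP 9.3.2 and 10.4.1, extend the planned NRI analysis of week 12 PASI 75, or add one mandatory sensitivity analysis, so that a subject is a non-responder at visits after starting another biologic, systemic or phototherapy treatment for psoriasis, whether or not a PASI is observed. Report it beside the as-observed primary result and repeat it for PASI 75 by reason for apremilast failure (SAP 10.4.5).

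Identify these subjects at the deviation and concomitant-medication review before database lock. State that psoriasis therapies are recorded through the last efficacy visit. Table 1 already lists concomitant medications to Week 24/ET, but the text of Protocol 6.3 and 7.3.9 stops at the end of treatment, so start dates are not assured for a subject who stops etanercept and stays on.

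**Cost.** SAP wording, one extra analysis, and a short clarification of data collection in the protocol or CRF instructions. The added analysis may give a slightly lower rate, and it understates the rate for any such subject who would have responded on etanercept alone; showing both results makes the gap between them visible.

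Making this rule the primary analysis, or extending it to ordinal and continuous endpoints, is optional and is the sponsor's choice of estimand.

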# 9.3.3 Missing Components of Composite Endpoints

Missing components will not be imputed. Missing composite endpoint at post-baseline will be imputed by carrying forward from the last non-missing post-baseline value for that endpoint.

### 9.4 Detection of Bias

Factors that may bias the results of the study include:

- major protocol deviations likely to impact the analysis
- investigational product dosing compliance
- reasons for early withdrawal from treatment and from study

The incidence of these factors will be assessed. Major protocol deviations likely to impact the analysis and interpretation of the efficacy endpoints will be summarized in the clinical study report (CSR). If a significant number of major protocol deviations are observed, an additional sensitivity analysis may be performed on efficacy data excluding subjects with major protocol deviations.

In addition, a summary of IP dosing compliance will be provided. A sensitivity analysis including subjects who completed all scheduled doses of IP may be performed on PASI 50, 75, and 90 responses and sPGA 0 or 1 response to assess the potential bias of IP compliance if a significant IP non-compliance issue is detected.

Reasons for early withdrawal from treatment and early withdrawal from study will be summarized. If a significant pattern is observed, additional sensitivity analyses may be performed on efficacy data adjusting for reasons for early withdrawal.

# 9.5 Outliers

Histograms will be examined to identify outliers in any of the continuous variables used in the analyses. Frequency tables of the categorical data used in the analyses will be examined to identify unexpected values.

Outliers due to data entry errors will be corrected by the study team before data lock. Outliers that are not due to data entry error will be included in the analysis. If it is deemed necessary after the team reviews the output from the planned analyses after data lock, a post-hoc sensitivity analysis excluding subjects with outliers may be performed.

# 9.6 Distributional Characteristics

Since efficacy endpoints will not be analyzed using parametric tests, assessment of the normality of the data will not be performed.

# 9.7 Validation of Statistical Analyses

Programs will be developed and maintained, and output will be verified in accordance with current risk-based quality control procedures.

Tables, figures, and listings will be produced with validated standard macro programs where standard macros can produce the specified outputs.

The production environment for statistical analyses consists of Amgen-supported versions of statistical analysis software, for example the SAS System version 9.2 or later.

# 10. Statistical Methods of Analysis

# 10.1 General Principles

The final analysis will be performed after all subjects have completed the week 24 assessments and all data through week 24 and the 30-day safety follow-up have been finalized.

Subject disposition, demographics, and baseline disease characteristics will be summarized descriptively for all subjects.

For efficacy analyses, 95% confidence intervals for estimated responses will be generated as descriptive statistics. All categorical endpoints will be summarized using number and percentage of subjects. In addition to being summarized using number and percentage of subjects, ordinal categorical endpoints will also be summarized using number of observations, mean, standard error, standard deviation, median, 1st quartile, 3rd quartile, minimum, and maximum. All continuous endpoints will be summarized using number of observations, mean, standard error, standard deviation, median, 1st quartile, 3rd quartile, minimum, and maximum.

The primary analysis for all efficacy endpoints will be performed using the full analysis set. Missing values will be imputed using post-baseline last observation carried forward method. A sensitivity analysis for the primary endpoint will be performed using non-responder imputation as described in Section 9.3.2. Sensitivity analyses on all the primary and secondary endpoints will be performed using observed cases as well. In addition, the primary endpoints may be examined using the covariates listed in Section 4.2. Summary statistics will be generated as well as confidence intervals and p-values as appropriate. No multiplicity adjustments will be made for the p-values.

Safety endpoints will be summarized descriptively for all subjects.

